10 PATIENT SAFETY

10.1 Monitoring of Adverse Events

Significant adverse events should be identified and recorded. Seriousness, expectedness, and causality will be assessed using the definitions that follow. The descriptions and grading scales found in the revised NCI Common Terminology Criteria for Adverse Events (CTCAE) version 4.0 will be utilized for adverse event reporting.

10.2 Definitions of Adverse Events and Causality

An **Adverse Event (AE)** is any untoward medical occurrence in a patient administered a pharmaceutical product and which does not necessarily have to have a causal relationship with the treatment. For marketed products in the U.S., a **Serious Adverse Event (SAE)** is any untoward medical occurrence that at any dose:

- Results in death (if the patient's death is suspected as being a direct outcome of the adverse event)
- Is life-threatening (the patient was at substantial risk of dying at the time of the adverse event or it is suspected that the use or continued use of the product would result in the patient's death)
- Requires inpatient hospitalization or prolongation of existing hospitalization
- Results in persistent or significant disability/incapacity
- Results in a congenital anomaly/birth defect (i.e., exposure to a medical product prior to conception or during pregnancy resulted in an adverse outcome in a child)
- Requires intervention to prevent permanent impairment or damage
- Overdosage (regardless of adverse outcome) of any study medication. An overdose is defined as the accidental or intentional ingestion of any dose of a product that is considered both excessive and medically important.
- Pregnancy
- Potential drug-induced liver injury(DILI): as defined by: **1:**ALT or AST elevation > 3 times upper limit of normal (ULN) **AND 2:** Total bilirubin > 2 times ULN, without initial findings of cholestasis (elevated serum alkaline phosphatase **AND 3:** No other immediately apparent possible causes of AST/ALT elevation and hyperbilirubinemia, including, but not limited to, viral hepatitis, pre-existing chronic or acute liver disease, or the administration of other drug(s) known to be hepatotoxic.

- Is an important medical event, defined as a medical event(s) that may not be immediately life threatening or result in death or hospitalization but, based upon appropriate medical and scientific judgment, may jeopardize the patient or may require medical or surgical intervention to prevent one of the other serious outcomes listed in the definition above. Examples of such events include, but are not limited to, intensive treatment in an emergency room or at home for allergic bronchospasm, or blood dyscrasias or convulsions that do not result in hospitalization.

The SAE reporting period begins following the subject's written consent to participate in the study through 100 days of discontinuation of dosing. AEs should be followed to resolution or stabilization, and reported as SAEs if they become serious. This also applies to patients experiencing AEs that cause interruption or discontinuation of investigational product, or those experiencing AEs that are present at the end of their participation in the study. Such patients should receive post-treatment follow-up as appropriate. If an ongoing AE changes in its severity or in its perceived relationship to study drug, a new AE entry for the event should be completed.

Additionally, any serious adverse event considered by an investigator to be possibly, probably, or definitely related to the investigational product that is brought to the attention of the investigator at any time outside of the time period specified in the previous paragraph also must be reported immediately to the IRB (only as required per local policy) and Bristol-Myers Squibb (BMS) designated pharmacovigilance representative.

Medical and scientific judgment should be exercised in deciding whether expedited reporting is appropriate in other situations, such as important medical events that may not be immediately life-threatening or result in death or hospitalization but may jeopardize the patient or may require intervention to prevent one of the other outcomes listed in the definition above. These should also usually be considered serious.

Note: The term "life-threatening" in the definition of "Serious Adverse Event" refers to an event in which the patient was at risk of death at the time of the event; it does not refer to an event that hypothetically might have caused death if it were more severe.

An **Unexpected Adverse Event** is not listed in the current US Package Insert may be mentioned in the package insert, but differs from the event because of greater severity or specificity.

Causality is a determination of whether there is a reasonable possibility that the drug may have caused or contributed to an adverse event. It includes assessing temporal relationships dechallenge/rechallenge information, association (or lack of association) with underlying diseases, and the presence (or absence) or a lack of one or more likely causes.

The Investigator must attempt to determine if an adverse event is in some way related to the use of the study drug. This relationship should be described as follows:

Unlikely: The event is clearly due to causes distinct from the use of the study drug, such as a documented pre-existing condition, the effect of a concomitant medication, a new condition which, based on the pathophysiology of the condition, and the pharmacology of the study drug, would be unlikely related to the use of the study drug.

Possible: The event follows a reasonable temporal sequence from administration of the study drug or the event follows a known response pattern to the study drug *BUT* the event could have been produced by an intercurrent medical condition which, based on the pathophysiology of the condition,

and the pharmacology of the study drug, would be unlikely related to the use of the study drug or the event could be the effect of a concomitant medication

Probable: The event follows a reasonable temporal sequence from administration of the study drug and the event follows a known response pattern to the study drug AND the event cannot have been reasonably explained by an intercurrent medical condition *or* the event cannot be the effect of a concomitant medication

Definite: The event follows a reasonable temporal sequence from administration of the study drug, the event follows a known response pattern to the study drug and based on the known pharmacology of the study drug, the event is clearly related to the effect of the study drug

Unknown: Based on the evidence available, causality cannot be ascribed

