5.2 Definition of Dose Limiting Toxicity

Patients will be monitored for safety by assessing toxicities as graded by the NCI CTCAE v4.0. Dose limiting toxicity (DLT) will be defined as one or more of the following toxicities considered to be at least possibly related to one of the study drugs during Cycle 1

- Grade 3 or greater nonhematologic toxicity with the exception of Grade 3 nausea, vomiting and diarrhea that responds to supportive therapy.
- Grade 4 thrombocytopenia, or grade 3 thrombocytopenia with bleeding, or any requirement for platelets transfusion
- Grade 4 neutropenia persisting for more than 5 days.
- Grade 3 or greater febrile neutropenia (temperature $\geq 38.5^{\circ}\text{C}$)
- Grade 4 anemia, unexplained by underlying disease

Patients that experience a lenalidomide-related hematologic DLT may continue on therapy if the event resolves, the investigator considers it in the best interest of the patient to continue and the patient qualifies for initiation of the next cycle with standard of care lenalidomide dose reduction.

Discontinuation of treatment due to disease progression will not constitute a DLT.

After 4 cycles of therapy or earlier if clinically indicated, response determination will be assessed by the IMWG criteria. At the end of Cycle 4, if a subject has responded (complete or partial response) or has stable disease, dosing with Nivolumab and lenalidomide will continue for a minimum of 8 additional cycles or until withdrawal.

If disease progression is observed at the end of Cycle 4 evaluation, all study therapy will be discontinued. Confirmation of progression of disease will be done according to the IMWG criteria.

Following the 30-day post-treatment follow-up assessment, additional evaluations will occur once per month (unless subject discontinued due to progression) until the earliest of the following events: disease progression, the time of initiation of new therapy, death or study completion.

Study completion is defined as 30 days after the last subject remaining on study medication discontinues study medication.

An independent Data Monitoring Committee will continue oversight of this trial.

Treatment will continue until Progression of disease, death, unacceptable toxicity or patient or treating physician decision to discontinue therapy.

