5.3.1 Early Stopping Rules

The study may be suspended or terminated prematurely with sufficient concern for excessive toxicity. Frequency, nature, and severity of adverse events will be reviewed by the PI and study team and compared to what is known about lenalidomide and nivolumab from other sources, including published literature, scientific meetings and discussion with Bristol Myers Squibb to determine if the trial should be terminated before completion. If n=3 subjects experience an infection of grade 3 and higher or an adverse event of grade 3 or greater which is determined to be immune-mediated, and possibly, probably or definitely related to nivolumab and/or lenalidomide, the study will be suspended to allow assessment of whether to continue further enrollment or terminate the trial. If any subject dies while getting treatment, enrollment will be halted to determine relationship to study drugs. Enrollment will resume if determined not to be related to study drugs. If determined to be related to study drugs, the study will be suspended to allow assessment of whether to continue further enrollment or terminate the trial. If N=3 dies and determined to be related to study drugs, the study will be terminated.

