		
In addition to the criteria for permanent discontinuation of Nivolumab based on CTC grade/severity, permanently discontinue Nivolumab for the following:
 
 • Recurrence of a previously experienced Grade 3 treatment-related AE following resumption of dosing 	
alternative etiology (e.g. disease progression, concomitant medications, infections, etc)
 
 • In the absence of a clear alternative etiology, all events should be considered potentially immune related • Symptomatic and topical therapy should be considered for any low grade events (Grade 1 or 2, unless otherwise specified)
Grade 1		No dose modification	
Grade 2		
Hold Nivolumab dose until grade 2 resolution to grade 1
 
 • If toxicity worsens then treat as Grade 3 or Grade 4 • If toxicity improves to baseline then resume treatment as seen best by treating physician • Nivolumab can be resumed once event stabilizes to grade 1 and 5-7 days have passed after completion of steroid taper. 
Subjects with endocrinopathies who may require prolonged or continued steroid replacement can be retreated with Nivolumab on the following conditions: 1) the event stabilizes and is controlled, 2) the subject is clinically stable as per investigator or treating physician's clinical judgement, and 3) doses of prednisone are at less than or equal to 10 mg/day or equivalent
	
 • For persistent (greater than 3-5 days) low grade (Grade 2) or severe (Grade \geq 3) events promptly start prednisone PO 1-2 mg/kg/day or IV equivalent • If symptoms recur or worsen during corticosteroid tapering (28 days), increase the corticosteroid dose (e.g. up to 2-4 mg/kg/day or IV equivalent) until stabilization or improvement of symptoms, then resume corticosteroid tapering at a slower rate ($>$ 28 days of taper) • More potent immunosuppressives such as TNF inhibitors should be considered for events not responding to systemic steroids • Discontinuation of Nivolumab is not mandated for Grade 3/4 inflammatory reactions attributed to local tumor response (e.g. inflammatory reaction at sides of plasmacytomas). Continuation of study drug in this situation should be based upon a benefit/risk analysis for that subject
Grade 3		Depending on the individual toxicity, may permanently discontinue Nivolumab	
Grade 4		Permanently discontinue Nivolumab	

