The proportion of responses (partial and complete) will be calculated out of all eligible patients who receive any treatment in that disease group who are included in the phase II assessment. Assuming the number of responses is binomially distributed, 95% binomial confidence intervals will also be calculated for the estimate of the proportion of responses. All adverse events will be summarized by the NCI CTCAE v. 4 criteria, and tabulated across all patients who received any treatment with a focus on severe (grade 3+) adverse events and toxicities (i.e. those deemed at least possibly related to study treatment). In addition, we will summarize the proportion of patients who received dexamethasone after being stable disease but without response after 2 cycles of therapy. We will descriptively summarize how many of these patients were converted to response after the addition of dexamethasone. Since the addition of dexamethasone is part of the overall treatment regimen that is dependent on treatment outcome at a certain time point, we will not make other adjustments to the study design to evaluate these patients separately outside of this descriptive summarization of whether or not they received the dexamethasone. We will evaluate other clinical outcomes such as progression-free survival and overall survival using the methods of Kaplan-Meier, although these analyses will be exploratory and primarily to help describe the cohort itself.

Correlative analyses will also be done, including analysis of markers of the immunogenicity of nivolumab. In particular, we will evaluate biological and cellular markers in patients treated with nivolumab, measure PD-L1 expression on MM cells, percentage increase in NK cell activity, migration, immune complex formation, and cytotoxicity. Other markers such as plasma cell IHC baseline expression to characterize immunologic markers of MM cells that are responsive to nivolumab such as TNF-alpha, IFN-gamma, CD4, CD8, and granzyme B will be evaluated in addition to markers of MM cells responsive to lenalidomide (Sparc, IRF-4). Changes in these markers before and after therapy will be explored using graphical analyses as well as summarized quantitatively. We will also explore how changes in these correlative markers may differ based on whether or not the patient achieved a response or not; to accomplish this, we will utilize different plotting characters and colors for successes

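### The causality scale in section 10.2 has no related level for a well-timed event with no other cause and no known drug pattern, so the event defaults to Unknown and misses the related-only counts

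*Combined protocol and SAP*

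**What the plan says.** Section 10.2 asks the investigator to assign one of five levels.

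- *Unlikely*: "The event is clearly due to causes distinct from the use of the study drug".
- *Possible*: reasonable timing or a known response pattern, then a capitalised BUT and a further condition, that "the event could have been produced by an intercurrent medical condition which, based on the pathophysiology of the condition", or that a concomitant medication could be responsible.
- *Probable*: reasonable timing and a known pattern, with no reasonable explanation from another condition or no concomitant medication effect.
- *Definite*: reasonable timing, a known pattern, and a clear drug effect.
- *Unknown*: "Based on the evidence available, causality cannot be ascribed".

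Four places use the scale as a threshold.

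- Section 5.2 limits DLTs to "toxicities considered to be at least possibly related to one of the study drugs during Cycle 1".
- Section 5.3.1 counts three subjects with grade 3 or higher infections, or grade 3 or higher events determined to be immune-mediated, that are "possibly, probably or definitely related to nivolumab and/or lenalidomide, the study will be suspended".
- Section 7.1.1 defines toxicities as "those deemed at least possibly related to study treatment".
- Section 10.2 requires SAEs outside the consent-to-100-day period to be reported if they are "possibly, probably, or definitely related to the investigational product".

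None of these places says how *Unknown* is handled.

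Two other statements point the other way. Just before the scale, section 10.2 describes causality as a reasonable possibility that the drug caused or contributed to the event, weighing timing, dechallenge and rechallenge, and whether other likely causes are present or absent. The overall-management row of Table 6.5.2 says: "In the absence of a clear alternative etiology, all events should be considered potentially immune related".

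**The concern.** A causality scale should not rate an event as less related when a competing explanation is removed. This one does. Take a new grade 3 event with plausible timing, no other cause and no established drug pattern. The missing alternative bars *Possible*, and the missing pattern bars *Probable* and *Definite*.

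This kind of event matters here. Section 1.5 describes other myeloma studies of nivolumab with lenalidomide or pomalidomide only as recruiting or in process, and the documents report no toxicity profile for this pair. An event with no recognised pattern and no other explanation is one that safety monitoring should pick up. More than one centre takes part, so an unassigned case also invites inconsistent coding.

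**Working it through.** The plan attaches no figure to this point, so there is none to reproduce. The check is logical, with one numerical illustration.

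**Step 1. Apply the definitions.** Take events that are neither clearly due to another cause (which would be *Unlikely*) nor clearly due to the drug (needed for *Definite*). The BUT clause is read as limiting both halves of *Possible*.

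| Reasonable timing | Known pattern | Another condition or medication could explain it | Level met |
|---|---|---|---|
| yes | yes | yes | *Possible* (also *Probable* if only one of the two kinds of alternative applies) |
| yes | yes | no | *Probable* |
| yes | no | yes | *Possible* |
| **yes** | **no** | **no** | **none; *Unknown* by default** |
| no | yes | yes | *Possible* |
| no | yes | no | none; *Unknown* by default |
| no | no | either | none; *Unknown* by default |

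The third and fourth rows differ only in whether an alternative explanation exists. Removing it takes the event from *Possible* to no related level at all. The mirror case (known pattern, poor timing, no other cause) also falls through.

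**Step 2. Trace the fourth row through each threshold.**

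| Place | Effect on the wording | Limit |
|---|---|---|
| 7.1.1 toxicities | Dropped from the related-only summary | All adverse events are tabulated whatever their attribution |
| 5.2 DLT | Not a DLT | DLTs feed no numerical rule in this trial |
| 5.3.1 suspension | Fails the relatedness condition | Matters only for an infection or an event determined to be immune-mediated |
| 10.2 late SAEs | No reporting duty through this sentence | All SAEs to 100 days are reported; section 10.3 has a separate reasonable-association route after the trial ends |

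**Step 3. Compare with the plan's other statements.** Good timing and no other likely cause are points that the general definition in 10.2 counts toward a reasonable possibility. Table 6.5.2 tells the investigator to treat the same event as potentially immune related. The five levels lead to neither result.

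**Step 4. Illustrate the effect on the suspension count.** Let n = 18 (section 5.4), p be the true proportion of subjects who should count, and u the share of those graded *Unknown*. Then q = p(1 − u), and the chance of three or more counted subjects is 1 − Σ C(18,k) q^k (1−q)^(18−k) over k = 0, 1, 2.

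- p = 0.20, u = 0: 1 − (0.0180 + 0.0811 + 0.1723) = 0.729.
- p = 0.20, u = 0.25, so q = 0.15: 1 − (0.0536 + 0.1704 + 0.2556) = 0.520.

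| Assumed p | u = 0 | u = 10% | u = 25% | u = 50% |
|---|---|---|---|---|
| 10% | 0.266 | 0.217 | 0.148 | 0.058 |
| 20% | 0.729 | 0.654 | 0.520 | 0.266 |
| 30% | 0.940 | 0.901 | 0.805 | 0.520 |

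The documents give neither p nor u. The model also treats a lost event as a lost subject, although a subject with any one attributed qualifying event still counts. The table shows direction only.

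**The case against.** **The gap depends on how *Possible* is parsed.** If the BUT clause limits only the known-pattern half, timing alone gives *Possible* and the main case is covered. The capitalised BUT makes that reading strained, and the mirror case would still fall through. The existence of two readings is itself a reason to clarify.

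***Unknown* is not defined as a residual category.** This is fair. Strictly, the event fits no label, and an investigator might fall back on the general definition in 10.2 and record *Possible*. But nothing says that the general definition overrides the levels, and an event with no label is no more countable than one labelled *Unknown*.

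**Table 6.5.2 is a safeguard, not a conflict.** It does push toward relatedness. It sits in a management table, however, and does not say how the event is coded under 10.2. One event could be managed as potentially immune related and still be coded *Unknown*.

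**The suspension rule rarely meets this case.** This largely stands. Table 6.5.2 lists recognised immune patterns, so an event without a pattern would seldom be determined immune-mediated. Infections usually have a competing explanation, given the immune compromise described in section 1.1, and so would be *Possible* and count. The relatedness condition in 5.3.1 may also apply only to the immune-mediated limb, although the comma favours both.

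**Deaths.** A reader might infer that a death of unknown causality escapes section 5.3.1. It does not: any on-treatment death halts enrollment, which resumes only if the death is determined to be unrelated. What is undefined is the next step.

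**Size.** A reader might start from the 5/27 (19%) grade 3 or higher figure for myeloma in section 1.4.2 and conclude that the trigger probability falls from 67% to 47% or 23% when 25% or 50% are graded *Unknown*. The arithmetic is right but the input is wrong. Those events were already attributed to nivolumab, and they are not limited to infections and immune-mediated events.

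**Conclusion.** The defect is real and narrow. Read literally, the scale places a well-timed, otherwise unexplained event with no known pattern below the same event with a competing explanation. That contradicts the general definition of causality in 10.2 and runs against Table 6.5.2. The conclusion rests on the natural reading of the BUT clause.

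The certain effects are on the related-only toxicity summary, the DLT label and the SAE duty beyond 100 days. The effect on the suspension rule is conditional and cannot be sized from the documents.

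A reader might infer that the trial could pass its suspension threshold unseen, or that such events vanish from the safety tables. The documents do not support either. All adverse events are tabulated, and all SAEs to 100 days are reported. The principal investigator's review (5.3.1, 10.6) and the data and safety monitoring committee's SAE review (10.6) are not limited by attribution. Those reviews are discretionary, though, and do not repair the numerical count.

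**What to change.** 1. In section 10.2, reword *Possible* so that an event with a reasonable temporal sequence and no clear alternative cause qualifies as at least *Possible*.
2. In the same section, state that *Unknown* is counted as at least possibly related for sections 5.2, 5.3.1 and 7.1.1 and for SAE reporting beyond 100 days, until another cause is documented.
3. Reconcile the levels with the general definition of causality in 10.2 and with the overall-management row of Table 6.5.2.
4. In section 5.3.1, reconcile the undefined step after a death graded *Unknown*. The existing halt on enrollment already covers the period before that decision.

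This is a wording amendment. Its cost is that some events later shown to be unrelated will count, so a pause for review becomes somewhat more likely and the reported toxicity rate slightly higher.
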